Survival Status											X ⁿ
Blood volume per visit (mL)	70	65	10	65	10	55	10	55	10		
Total blood volume	70	135	145	210	220	275	285	340	350		

Abbreviations: AE = adverse event, CT = computed tomography; ECG = 12-lead electrocardiogram; ECOG = Eastern Cooperative Oncology Group; HepB = hepatitis B; HepC = hepatitis C; HIPAA = Human insurance Portability and Accountability Act; HIV = Human immunodeficiency Virus; SAE = serious adverse event.

[figure not shown]
a. A window of ±3 days is permitted for Visits 3 through 9. Follow-up phase visits (Visits 10+) will be permitted a window of ±4 days, Tumor assessments will be permitted a window of ±1 week.

Immune Design
CMB305 (LV305 and G305) and Atezolizumab
Protocol IMDZ-C232; Version 03, Release Date 08Mar2017

[figure not shown]
- b. Patients will be followed with visits every 3 weeks (± 4 days) for 2 years (from Day 0) for atezolizumab treatment until progression. Tumor size will be assessed every 6 weeks for the first year, then every 12 weeks until progression. Patients will then have no further staging procedures. Tumor biopsies will be obtained at 6 months or longer for patients with treatment response. Tumor biopsies will also be obtained at time of progression.
- c. Informed consent and HIPAA authorization must be signed before any screening study-related procedures are initiated. Three informed consents will be used: one to screen tumor sample for NY-ESO-1, one to engage in the study protocol, and an agreement to continue in the study if the patient meets the criteria for progressive disease but wishes to remain on study.
- d. Documentation of NY-ESO-1 expression in prior tumor samples may have been collected from any procedure performed before baseline activities. There is no time limit for use of the results from the IMDZ-approved central lab.
- e. Vital sign measurements include temperature, pulse, respiratory rate, and resting systolic and diastolic blood pressure. On the day of each dosing, vital signs will be obtained pre-dosing and 30 minutes after dosing. For the first atezolizumab infusion, the patient's vital signs (HR, respiratory rate, BP, and temperature) should be measured within 15 minutes of the infusion, during the 60-minute infusion (every 15 \pm 5] minutes), and 30 minutes after the infusion. For subsequent infusions, vital signs do not need to be obtained during the infusion if the prior infusion was tolerated without symptoms.

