- f. Once the baseline physical exam has been conducted, a simple symptom-directed physical exam should be performed for all subsequent visits. Height and weight will be collected at Day 0 only.
- g. Imaging will be performed by CT scan as defined by RECIST/irRC at screening and every 6 weeks after first study injection for the first year, then every 12 weeks for tumor staging until disease progression and includes a confirmatory scan performed at least 4 weeks later. MRI, bone scans or PET/CT at baseline or subsequent visits will be performed only if clinically indicated.
- h. Blood for immunogenicity will be collected at clinical sites that are trained in peripheral blood mononuclear cells (PBMC) isolation. Baseline samples will be drawn twice to ensure a good yield. At least 55 mL should be collected in 8 Cell Preparation Tubes (CPT)TM tubes for T-cell response assays. See the Lab Manual for processing details.
- i. Initial safety labs are to be performed within 4 days before treatment initiation. On treatment days during the study dosing period, the hematology and clinical chemistry laboratories must also be performed and reviewed before dosing and may be performed up to 48 hours prior to the planned dosing.
- j. Thyroid function tests (triiodothyronine [T₃], thyroxine [T₄], and thyroid stimulating hormone [TSH]) should be taken at initial screening and at least every 3 months while being treated with atezolizumab. As thyroid disorders could occur at any time as a result of atezolizumab treatment, patients should be monitored for changes in thyroid function for clinical signs and symptoms of thyroid disorders (at the start of treatment, periodically during treatment, and as indicated based on clinical evaluation).
- k. Urine pregnancy test must be performed for women of childbearing potential within 72 hours before study drug administration and negative before study drug administration, including during the follow-up period if atezolizumab administration is continued. Serum pregnancy test may be performed if the site's standard operating procedures allow.
- l. Atezolizumab should be continued every 3 weeks for 2 years (from Day 0) or until disease progression unless toxicity occurs.

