- m. The pre-treatment biopsy must be completed ≤ 6 months prior to screening; if not available, a fresh biopsy may be included in the screening process. The tissue biopsy taken on Day 98 can be performed ± 2 weeks from this study visit; however, the patient may opt out of the Day 98 biopsy after a discussion with a physician and documentation in the patient's chart. If a tumor biopsy is not feasible, a biopsy may be done at a subsequent visit with approval provided by the Sponsor.
- n. Once patients have progressed and study drugs are discontinued for more than 30 days, their physicians will be contacted by the sites every 3 months by telephone until the study is completed (last patient, last death in the study) to assess OS. The attending physician will be contacted quarterly until study completion for identification of subsequent treatments and survival status.

Figure 1 Dosing Schedule for Each Treatment Arm

A. Combination Treatment Arm

B. Control Arm

Abbreviations: PBMC = peripheral blood mononuclear cell; CPI = checkpoint inhibitor.

Red syringe = LV305 injections; Green arrows = G305 injections; blue antibodies indicate atezolizumab treatment days.

The combination treatment arm will consist of administration of CMB305 and atezolizumab (A). Dosing of CMB305 (LV305 and G305) will occur every 2 weeks beginning with the administration of 2 consecutive doses of LV305 followed by alternating administration of G305 and LV305 for 12 weeks (i.e. during the Treatment Phase). Atezolizumab will be administered every 3 weeks. The control arm (B) will receive atezolizumab alone every 3 weeks.

Note: For the combined treatment arm (A), the trial will be conducted in 4 phases: Treatment Phase (study Days 0 to 84), Booster Phase (post Day 84 to 1 year post Day 0), Maintenance Phase (from 1 year to 2 years post Day 0), and Survival Follow-up Phase (quarterly thereafter). For the control arm (B), the trial will be conducted in 3 phases: Treatment Phase (study Days 0 to 84), Maintenance Phase (post Day 84 to 2 years post Day 0), and Survival Follow-up Phase (quarterly thereafter). Dosing with atezolizumab may continue up to 2 years until confirmed progression in both treatment arms. G305 may be given every 6 weeks following the Day 84 dose for up to 1 year (from Day 0) as a booster injection during the restaging follow-up visits.

TABLE OF CONTENTS

INVESTIGATOR AGREEMENT PAGE	2
STUDY SYNOPSIS	4
TABLE OF CONTENTS	22
LIST OF TABLES	27
LIST OF FIGURES	27

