8.2.3 Post-CMB305 Long-term Treatment Study Visits

Following the Treatment Phase, patients in the combined treatment arm will enter the Booster Phase (post Day 84 to 1 year post Day 0); patients who complete the Booster Phase will then enter the Maintenance phase (1 year to 2 years post Day 0). Patients in the control arm will enter the Maintenance Phase (post Day 84 to 2 years post Day 0).

8.2.3.1 Booster Phase (Combined Treatment Arm Only: post Day 84 to 1 year post Day 0)

The following procedures will be performed in the combined treatment arm during these visits:

1. AEs and SAEs (including MEOIs)
2. Concomitant Medications
3. Vital Signs
4. Physical examination: simple targeted examination
5. ECOG status
6. A G305 booster will be given in the combined treatment arm 6 weeks following the Day 84 dose and every 6 weeks thereafter for 1 year (from Day 0) or until disease progression.
7. Atezolizumab administration will be administered on Day 105 and every 3 weeks thereafter for 1 year (from Day 0) or until toxicity develops or progression. After Day 105, one of three atezolizumab doses may be delayed by 1 week (28 days instead of 21 days for one cycle) to allow for vacations.
8. Urine pregnancy test must be performed for FCBP within 72 hours before study drug administration and negative before study drug administration, if patients are still receiving booster doses of G305 and/or atezolizumab.

Blood samples for cellular immunity (55 mL) and a tumor biopsy will occur on Day 98 (\pm 2 weeks) and the following procedures will occur on Day 105:

- 12-lead ECG
- Blood for safety laboratory evaluations (10 mL)
- Urine pregnancy test for FCBPs
- Administration of atezolizumab

All subjects will return to the clinic every 3 weeks for 1 year (from Day 0) or until disease progression (whichever is later) for the following assessments:

1. AEs and SAEs (including MEOIs; only those possibly related to study drug will be reported)
2. Concomitant Medications (only those related will be reported)
3. Vital Signs
4. Physical Examination (symptom-specific)
5. ECOG status
6. Blood for safety laboratory evaluations (10 mL)
7. Thyroid function tests should be monitored at least every 3 months
8. Tumor staging by CT every 6 weeks for the first year, then every 12 weeks

The following procedures will occur at select study visits according to the study visit schedule provided in [Table 1](#):

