- A tumor biopsy should be performed at 6 months or longer (for patients with treatment response) and at the time of progression
- A blood sample will be collected at Day 168 for HIV testing (5 mL).
- Blood samples will be collected at Day 168

8.2.3.2 Maintenance Phase (Combined Treatment Arm: From 1 Year to 2 Years Post Day 0; Control Arm: Post Day 84 to 2 Years Post Day 0)

The following procedures will be performed these visits:

1. AEs and SAEs (including MEOIs)
2. Concomitant Medications
3. Vital Signs
4. Physical examination: simple targeted examination
5. ECOG status
6. For patients in the control arm, atezolizumab administration will be administered on Day 105 and every 3 weeks thereafter for 1 year (from Day 0) or until toxicity develops or progression. After Day 105, one of three atezolizumab doses may be delayed by 1 week (28

days instead of 21 days for one cycle) to allow for vacations. For patients in the combined treatment arm, atezolizumab administration will continue to be administered every 3 weeks for 1 year (from 1 year to 2 year post Day 0) or until toxicity develops or progression.

7. Urine pregnancy test must be performed for FCBP within 72 hours before study drug administration and negative before study drug administration, if patients are still receiving booster doses of G305 and/or atezolizumab.

For patients in the control arm, blood samples for cellular immunity (55 mL) and a tumor biopsy will occur on Day 98 (\pm 2 weeks) and the following procedures will occur on Day 105:

- 12-lead ECG
- Blood for safety laboratory evaluations (10 mL)
- Urine pregnancy test for FCBPs
- Administration of atezolizumab

All subjects will return to the clinic every 3 weeks for the following assessments:

1. AEs and SAEs (including MEOIs; only those possibly related to study drug will be reported)
2. Concomitant Medications (only those related will be reported)
3. Vital Signs
4. Physical Examination (symptom-specific)
5. ECOG status
6. Blood for safety laboratory evaluations (10 mL)
7. Thyroid function tests should be monitored at least every 3 months
8. Tumor staging by CT every 6 weeks for the first year, then every 12 weeks

The following procedures will occur at select study visits according to the study visit schedule provided in [Table 1](#):

- A tumor biopsy should be performed at 6 months or longer (for patients in the control arm with treatment response) and at the time of progression

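### Protocol Section 8.2.3.2 item 6 stops control-arm atezolizumab at 1 year while continuing it to year 2 in the combination arm, contradicting the 2-year limit stated for both arms elsewhere

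*Protocol*

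**What the plan says.** Section 8.2.3.2 lists the Maintenance Phase procedures for both arms. Item 6 sets atezolizumab dosing separately by arm.

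- Control arm: "For patients in the control arm, atezolizumab administration will be administered on Day 105 and every 3 weeks thereafter for 1 year". The item counts the year from Day 0 and allows an earlier stop for toxicity or progression.
- Combination arm: "atezolizumab administration will continue to be administered every 3 weeks for 1 year (from 1 year to 2 year post Day 0", with the same earlier stops.

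The heading above item 6 gives a different period for the control arm: "Control Arm: Post Day 84 to 2 Years Post Day 0". Section 8.2.3 introduces the phase in the same terms: "Patients in the control arm will enter the Maintenance Phase (post Day 84 to 2 years post Day 0".

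The control-arm schedule agrees with the heading. Protocol Table 2 note b sets 3-weekly visits "for 2 years (from Day 0) for atezolizumab treatment until progression", and note l reads: "Atezolizumab should be continued every 3 weeks for 2 years (from Day 0) or until disease progression unless toxicity occurs". The Figure 1 note covers both arms at once: "Dosing with atezolizumab may continue up to 2 years until confirmed progression in both treatment arms".

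**The concern.** Item 6 is current, arm-specific dosing text in the section that sites use to run visits. Read alone, it gives the two randomized arms different durations of the shared backbone drug. The trial asks what CMB305 adds to atezolizumab, so the arms should differ only in CMB305. If atezolizumab stopped at month 12 in one arm only, later differences in OS, PFS or time to next treatment could reflect the vaccine regimen, the extra year of atezolizumab, or both. A control patient still benefiting at month 12 could also lose treatment that the rest of the protocol provides.

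**Working it through.** **Step 1: compare every statement of control-arm duration.**

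| Place | Control-arm atezolizumab |
|---|---|
| Protocol 8.2.3.2 item 6 | 1 year from Day 0 |
| Protocol 8.2.3.2 heading; Section 8.2.3 | Maintenance Phase to 2 years |
| Protocol Table 2 notes b and l | 2 years from Day 0 |
| Protocol Figure 1 note | up to 2 years, both arms |
| Protocol 5.2 | up to 2 years, both arms |
| Protocol 5.7 | Day 84 to 2 years |
| SAP Figure 1 note; SAP Table 2 note l | 2 years |
| Protocol 5.1; SAP 3.1 Part 2 | up to 2 years, not limited to one arm |
| Protocol 7.2 | no calendar limit; progression or unacceptable toxicity |

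Only item 6 gives 1 year.

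**Step 2: look for a reading that reconciles item 6.** The 1 year might be meant to cover only the first part of maintenance. But the sentence that continues dosing into year 2 is expressly limited to the combination arm, so item 6 provides no control-arm dosing after month 12.

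**Step 3: likely origin (inference).** Booster Phase item 7 in Section 8.2.3.1, which applies only to the combination arm, reads: "Atezolizumab administration will be administered on Day 105 and every 3 weeks thereafter for 1 year (from Day 0". One year is right there, because a maintenance year follows. The control-arm sentence in item 6 nearly repeats it. The same subsection also assigns Day 168 HIV testing and LV305 persistence sampling to the control arm. Table 2 marks HIV testing at screening only and has no LV305 persistence row. That pattern fits text carried over from the other arm.

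**Step 4: scheduled doses.** With dosing every 21 days from Day 0 and no delays, the maximum number of doses by day D is floor(D/21) + 1.

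- To 1 year: floor(365/21) + 1 = 17 + 1 = 18.
- To 2 years: floor(730/21) + 1 = 34 + 1 = 35.
- Difference: 35 − 18 = 17. These are the doses at weeks 54, 57, …, 102, and (102 − 54)/3 + 1 = 17.

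**Step 5: which analyses fall after month 12.** Protocol 10.2.2.6.1 lists OS at 6, 12, 18 and 24 months and PFS at 3 and 12 months. Of these, only OS at 18 and 24 months falls after month 12. The 6-month PFR and the futility rule come earlier. Log-rank comparisons of OS, PFS and time to next treatment use all follow-up, so their later part could be affected.

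**Step 6: illustration of the number progression-free at month 12.** Protocol 10.3.1 says PFS with atezolizumab in this setting is unknown. Its benchmark medians of 3 months (unacceptable) and 5.2 months (desirable) are used here only as an assumed range, with S(t) = 0.5^(t/m).

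- m = 3: S(12) = 0.5^4 = 0.0625, and 0.0625 × 40 = 2.5 patients.
- m = 5.2: S(12) = 0.5^(12/5.2) = 0.202, and 0.202 × 40 = 8.1 patients.

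**The case against.** The strongest reply is that the protocol already leads sites to the right answer. Section 8.1, which opens the visit instructions, refers them to Tables 1 and 2 for visit timing and procedures. Section 7.2 also sends dosing to those tables, and Table 2 note l says 2 years. The heading directly above item 6 says the same.

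Most of this stands. It establishes the intent and makes a literal 1-year stop less likely. It does not remove the conflict. Section 9.1 describes the tables as the summary and Section 8.2 as the detail; that sentence concerns assessments, but it gives a coordinator a reason to read Section 8.2 as the fuller text. No rule says which protocol section governs. The precedence clause in SAP Section 8 concerns the statistical analysis, not dosing.

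It is also fair to say that little inference depends on this. The primary analysis is Kaplan-Meier estimation within each arm, between-arm comparisons are exploratory, and p-values are nominal.

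Several stronger readings are tempting but unsupported:

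- A reader might infer that the control arm was meant to receive 1 year, or that it will in practice. Nothing outside item 6 supports the first, and the documents do not show the second.
- A reader might take 2.5 to 8 of 40 as the number who would lose treatment. Progression-free is not the same as on treatment: Section 6.3 allows dosing past progression in some patients, while toxicity and withdrawal remove others. The range bounds exposure in neither direction.
- A reader might extend the PFS curve to month 18. The planned landmarks after month 12 are for OS, so such a count matches no planned analysis.
- A reader might argue that Section 6.3 settles the matter because month 12 is not a mandatory reason to stop. Month 24 is not listed either, so its silence does not separate 1 year from 2.

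**Conclusion.** The inconsistency is real and should be corrected. Item 6 is a wrong dosing rule in current text, contradicted by every other place that states a calendar limit applying to the control arm.

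The harm is conditional on a site following item 6 over Table 2. In that case a control patient still on treatment at month 12 would lose up to 17 scheduled infusions, assuming a strict 21-day schedule without delays. Comparisons after month 12 could then be confounded. Whether stopping at 1 year changes OS or PFS, and by how much, cannot be derived from the documents. The month-12 range of about 2.5 to 8 of 40 rests on exponential PFS and on medians that are design benchmarks, not forecasts for the control arm.

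This is not a flaw in the design, the sample size or the planned analyses.

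**What to change.** In the control-arm sentence of Section 8.2.3.2 item 6, replace the 1-year limit with 2 years from Day 0, keeping the existing stops for toxicity and progression. Notify sites that Table 2 notes b and l govern control-arm atezolizumab.

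Two optional additions are worth making in the same edit: state the 2-year limit in Section 7.2, and correct the control-arm HIV and LV305 persistence entries in Section 8.2.3.2 to match Tables 1 and 2.

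The cost is a one-sentence protocol correction and a site memo. Sample size, endpoints and analyses do not change.

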8.2.4 Survival Follow-up Phase (Post-Maintenance Phase Long-Term Quarterly Follow-up)

Following radiographic disease progression and discontinuation of study drugs for more than 30 days, patients will be followed-up by quarterly telephone calls to the attending physician or database search until study completion for survival status and subsequent treatment.

9.0 ASSESSMENTS OF EFFICACY AND SAFETY

9.1 Timing of Assessments

The timing of study assessments is summarized in the Schedules of Events for each treatment arm ([Table 1](#) and [Table 2](#)) and detailed in [Section 8.2](#) (Study Conduct). After five cycles of atezolizumab administration, one of three cycles may be delayed by 1 week (28 days instead of 21 days for one cycle) to allow for vacations.

9.2 Demographics, Medical History, and Baseline Characteristics

Medical history includes previous clinically significant diseases, surgeries, cancer history and therapies, responses to prior therapies and medications used by the patient within 28 days prior to screening. Demographic information will include age, sex, race, ethnicity, etc. ECOG Performance status will be assessed using standard methodologies and criteria outlined in [Appendix A](#).

9.3 Efficacy Assessments

9.3.1 Tumor Response Based upon RECIST and irRC

Tumor staging by CT will be performed every 6 to 9 weeks and images/scans will be evaluated by the sites for treatment decisions and later by BICR for tumor responses. The RECIST v1.1 criteria modified to use irRC³⁷ will be used to determine disease progression as defined in [Appendix C](#). The irRC also require a confirmation of CR/PR/PD at least 4 weeks later with imaging. Once confirmed, the date of progression will be defined as the first date that the total tumor burden was shown to have increased by at least 20% compared with nadir. For this study, the modified irRC using unidimensional measurements of the tumor will be implemented (see [Appendix C](#) and [Appendix D](#)). Evaluations will be used for determination of PFR, PFS, ORR, DOR, and time to response. OS will also be evaluated.

9.3.2 Immune Response

The following exploratory immune monitoring will be conducted:

- Cellular immunogenicity as measured by changes from baseline and over the course of the trial period in peripheral blood levels of T cells, T-cell effector and memory populations, and T-cell associated cytokine production.
- Humoral immunogenicity as measured by changes from baseline and over the course of the trial period with anti-NY-ESO-1 antibodies or TAAs.
- Evaluation of dosing response by RNA profiling of PBMCs as measured by the changes from baseline.

Details for sample handling and assay performance will be provided in the Immune Monitoring Manual.

9.3.3 Exploratory Biomarkers

Pre-, on-, and post-treatment blood or tumor samples may be collected for exploratory analyses of potential biomarkers of CMB305 or atezolizumab immunogenicity and clinical tumor response. A number of exploratory analyses are being investigated, but the predictive value of such tests is not yet known. The data collected from these exploratory tests will help to define a set of biomarkers that might be used in future studies to help define the ability of CMB305 to stimulate antitumor immune responses, to help stratify patients who might respond to these treatments, and/or to determine a minimum therapeutic dose. Exploratory blood tests may include functional assays of cytolytic T cells or other immune cells directed against autologous tumor cells or surrogate target cells, modifications of current assays to detect antitumor cellular immunity, detection or analyses of circulating tumor cells, and/or analyses of other (as of yet undefined) tumor markers and immune function.

Pre- and on-study cancer biopsy tissue will be examined for evidence of antitumor cellular immunity (e.g., CD8 T cell or NK cell infiltration, tumor necrosis, etc.) and for evidence of immune suppression within the tumor microenvironment. Blood or tumor samples will only be used to examine the patient's immune response, their cancer, or to help evaluate any potential toxicity arising in the study. The samples will not be examined for unrelated research or diseases.

